96 establishing the first diagnostic criteria for BED [2]. BED is a serious psychiatric condition that
97 often co-occurs with mood, anxiety, and/or substance abuse disorders [3,4]. In the Diagnostic
98 and Statistical Manual 5 (DSM 5)[5], the Feeding and Eating Disorders section has been revised
99 and expanded. BED previously was categorized under eating disorder not otherwise specified
100 (ED-NOS), but is now a stand-alone disorder. With this new recognition, it is likely that more
101 patients will be seeking treatment, and, consequently, more healthcare providers will need
102 efficacious treatments for BED.

103

104 BED is characterized by the consumption of an objectively large amount of food in a short
105 period (≤ 2 hours), accompanied by feeling a loss of control over eating [5]. Persons typically eat
106 more rapidly than usual, eat until uncomfortably full, eat large amounts when not physically
107 hungry, eat alone due to embarrassment, and feel disgust or upset about these episodes after they
108 occur. Binge episodes must occur once per week for an average of 3 months for a diagnosis of
109 BED. The prevalence of BED in the general population is 1.6% of women and 0.8% of men,
110 based on DSM-IV criteria [6], but these numbers will likely increase given the decreased
111 threshold to one binge episode required per week (as compared to the previous criteria of two
112 episodes per week). For example, a recent study of a representative sample of Australian late
113 adolescents and adults reported a prevalence range of 5.6 – 6.9% for BED using the DSM 5
114 diagnosis [7]. The prevalence also increases as body mass index (BMI) increases including
115 persons seeking weight loss treatment [8] and those seeking bariatric surgery [e.g., 9]. BED is
116 also associated with significant health complications independent of BMI, including increased
117 risk for chronic neck and back pain, diabetes, hypertension, and chronic headaches [10].

118

119 As stated above, persons with BED are more likely to have co-morbid psychiatric diagnoses,
120 such as mood disorders, anxiety disorders, and substance use disorders as compared to persons
121 without an eating disorder [4]. A recently published meta-analysis has also confirmed that
122 quality of life is significantly lower among individuals with BED as compared to those without it
123 [11]. Treatment for BED often improves co-morbid mood and anxiety symptoms, as well as
124 quality of life [12].

125

126 Aside from the core behavior of engaging in binge episodes, BED is associated with a range of
127 eating disordered attitudes and behaviors. Previous studies have established that persons with
128 BED experience higher levels of disinhibition over eating and perceived hunger [13]. In
129 addition, food cravings are often extreme among those with BED, typically described as
130 experiencing obsessions with food and feeling compelled to act on those thoughts. Thus, these
131 extreme thoughts regarding food interfere with one's ability to resist binge episodes. Successful
132 treatment of BED should help improve these psychological correlates of disordered eating
133 behavior, as well as reduce the actual occurrence of binge episodes. However, data regarding the
134 impact of liraglutide has not been published (to our knowledge) that demonstrate its impact on
135 these psychological factors related to eating behavior.

136

137 Lisdexamfetamine is the only medication currently approved by the FDA for the treatment of
138 BED [14], although other medications, including selective serotonin re-uptake inhibitors (SSRIs)

139 [15-16], topirimate [17], and sibutramine [18] have been tested for this disorder. McElroy and
140 colleagues tested several dosing levels of lisdexamfetamine as compared to placebo, using a 3-
141 week titration period and 8 week trial at full strength. They found reductions in the frequency of
142 binge episodes per week for placebo and the 30-, 50-, and 70-mg/d treatment groups of [mean
143 (SD)] -3.3 (2.04), -3.5 (1.95), -4.1 (1.52), and -4.1 (1.57), respectively. These reductions were
144 significantly greater in the 50- and 70-mg/d groups as compared to placebo. The percentage of
145 participants who achieved cessation from binge episodes for four weeks at the end of the trial
146 was 42% of those on placebo vs. 50% across all treatment groups. Reductions in body weight
147 were -0.1 (3.09), -3.1 (3.64), -4.9 (4.43), and -4.9 (3.93) kg for placebo, and the 30-, 50-, and 70-
148 mg/d groups, respectively. (All treatment groups differed significantly from the placebo group.)
149

150 Examining the effects of a weight loss agent, sibutramine (15 mg/d), as compared to placebo
151 over 24 weeks, Wilfley et al. showed significant reductions in binge episodes per week among
152 those taking sibutramine, with a mean (SD) of -2.7 (1.7) as compared to -2.0 (2.3) for those on
153 placebo [18]. (Our study physician, [name] was an investigator for this trial.) Of those on
154 sibutramine, 58.7% achieved cessation of binge episodes for four weeks as compared to 42.8%
155 of the placebo group. Weight loss was also significantly greater in the sibutramine group with a
156 mean (SD) = - 4.3 (4.8) kg as compared to that with placebo, +0.8 (3.5) kg.
157

158 However, sibutramine is no longer available on the market in Europe or the United States due to
159 medical complications. Randomized controlled trials of some SSRIs have shown significant
160 reductions in binge episodes per week as compared to placebo, but weight loss has not generally
161 been significant or long-lasting on these agents. In addition, sexual functioning is often adversely
162 impacted on SSRI agents. While topiramate has shown successful reductions in both binge
163 episodes and weight [17], its side effect profile, particularly its negative effect on cognitive
164 functioning, often makes this medication difficult to tolerate. Thus, more medications are needed
165 that produce significant reductions in binge eating, as well as weight, among this population.
166

167 In sum, BED is a serious disorder associated with distress and medical co-morbidities. Cognitive
168 behavior therapy is considered the most effective treatment for BED [19], but it is expensive,
169 time-consuming, and not available in many geographical regions. Thus, effective
170 pharmacotherapies are needed for this patient population, particularly medications that do not
171 increase weight or negatively affect sexual functioning, as found with SSRIs, or cognitive
172 functioning, as often seen with topiramate. Finally, as a stimulant, lisdexamfetamine poses the
173 potential for abuse, which may be problematic for a significant proportion of persons with BED,
174 given the elevated rate of substance use disorders among persons with BED [3,4].
175

176 The proposed study will test the efficacy of liraglutide 3.0 mg/d (Saxenda) for the treatment of
177 BED. Although data do not seem available regarding liraglutide's effect on dampening the drive
178 to eat in previously published weight loss trials [20, 21], there is some evidence that liraglutide
179 could help significantly reduce the urge to engage in binge eating, and also suppress appetite.
180 Only one previous study has tested liraglutide in the treatment of BED, to our knowledge [22].
181 This study was an open-label administration of liraglutide 1.8 mg/d with minimal diet and
182 lifestyle advice, as compared to diet and lifestyle advice only among patients in Malaysia. BED
183 symptoms were assessed with the self-reported Binge Eating Scale (BES) [23]. Participants
184 assigned to liraglutide significantly decreased their BES scores at 6 and 12 weeks (study end).

185 These participants also showed significant decreases in weight (95.5 to 90.1 kg), waist
186 circumference, systolic blood pressure, fasting glucose, and total cholesterol. However, there
187 were several weaknesses with this study, including its lack of a placebo group and its reliance on
188 a global self-report measure of binge eating, as compared to specific assessment of the frequency
189 of binge episodes per week. As such, a randomized controlled trial (RCT) would be a logical
190 next step to test whether liraglutide 3.0 mg/d is superior to placebo.

191

192

193 SPECIFIC OBJECTIVES:

194 Primary Objective:

195 To test the efficacy of liraglutide 3.0 mg/d as compared to placebo in reducing the number of
196 binge episodes per week during a 17-week, randomized, placebo-controlled trial.

197

198 Secondary Objectives:

199 To compare the proportion of participants on liraglutide 3.0 mg/d as compared to placebo who
200 achieve remission from binge episodes at week 17, defined as having no binge episodes for the
201 previous 4 weeks.

202

203 To compare differences between the liraglutide 3.0 mg/d and placebo groups in changes in body
204 weight, global BED symptom improvement, cognitive restraint of food intake, dietary
205 disinhibition, perceived hunger, quality of life, and depressed mood at treatment end.

206

207 *Of note: the Eating Inventory (cognitive restraint of food intake, dietary disinhibition, and
208 perceived hunger) was administered at baseline and at study end. With the small number of
209 completers, it may not be possible to run the mixed models analyses on these outcome variables.*

210

211 RESEARCH DESIGN AND METHODS

212 Study Hypothesis (hypotheses):

213 The trial has the following **primary aim and hypothesis**:

214 **Aim 1.** The primary aim is to test the efficacy of liraglutide 3.0 mg/d in reducing the number of
215 binge episodes per week during a 17-week, randomized, placebo-controlled trial.

216

217 **H₁:** We hypothesize that participants randomized to liraglutide 3.0 mg/d (n =76) will show
218 significantly greater reductions in the number of binge episodes per week as compared to those
219 on placebo (n = 76).

220

221 *Of note, the final sample size is n=36 total.*

222

223 The trial has the following **secondary aims and hypotheses**.

224

225 **Aim 2.** We will compare the proportion of participants in the two groups who achieve remission
226 from binge eating at week 17, defined as having no binge episodes for the previous 4 weeks.

227

228 **H₂:** We hypothesize that significantly more participants in the liraglutide 3.0 mg/d group will
229 achieve remission at week 17 as compared to the placebo group.

230
231 **Aim 3.** We will compare differences between the liraglutide 3.0 mg/d and placebo groups in
232 changes in body weight, global improvement BED symptom improvement, cognitive restraint of
233 food intake, dietary disinhibition, perceived hunger, quality of life, and depressed mood at week
234 17.

235
236 **H₃:** We hypothesize that participants randomized to liraglutide 3.0 mg/d as compared to those
237 assigned to placebo, will lose significantly more weight, and show greater improvements in
238 investigator-rated global BED symptoms, cognitive restraint of food intake, dietary disinhibition,
239 hunger, quality of life, and depressed mood. (We note that these latter comparisons, Aims 2 and
240 3, are considered exploratory. The study is not powered to determine significant differences
241 among groups on these outcomes.)

242
243 *We note that the Eating Inventory subscales (restraint, disinhibition, and hunger) were*
244 *completed at baseline and treatment end only, and we may not have enough completers to run*
245 *the final analyses for this secondary outcome.*

246
247 **Endpoints:**

248
249 **Primary**

250
251 The primary endpoint is change in binge episodes per week from randomization (week 0) to
252 study end (week 17).

253
254 **Secondary**

255
256 The secondary endpoints include examining the proportion of participants who have achieved
257 remission from binge-eating (no binge episodes between weeks 13 – 17), week 17 rating on the
258 interviewer-based Clinical Global Impression of Improvement Scale (CGI-I)[24] for global
259 assessment of BED symptoms, and changes in body weight, cognitive restraint of food intake,
260 dietary disinhibition, perceived hunger, quality of life, and depressed mood.

261
262 *(See note above regarding restraint, disinhibition, and hunger variables.)*

263
264 **Study type:**

265
266 We propose a 17-week, single-center, double-blind, randomized placebo-controlled trial with
267 parallel groups. There are two treatment arms: a) liraglutide titrated over 5 weeks to 3.0 mg/d,
268 followed by 12 weeks on full dose, and b) placebo for the full 17 weeks. Seventy-six
269 participants will be randomized to each of the two groups, for a total of 152 participants with
270 BED.

271
272 *Of note, the final sample size for analyses will be 36 participants.*

273
274
275

276 **Rationale for Study Design**

277

278 We have considered the design of this study at length based on the literature and our group's
279 experience with clinical trials for BED [e.g. 18, 25]. Most previous RCTs for BED, and
280 certainly all of the initial trials for each individual agent, have used a simple double-blind,
281 randomized placebo control design to demonstrate efficacy [see 26 for review]. Cross-over
282 designs have not been used in any of these trials to date. As reviewed above, only one open label
283 trial of liraglutide 1.8 mg/d has been published [22], so this would be the first placebo-controlled
284 trial testing the efficacy of liraglutide for BED.

285

286 Of note, previous studies have shown 30 – 60% of persons with BED are responsive to placebo.
287 Those with mild symptom profiles tend to be most susceptible to placebo response [27].
288 Therefore, many BED trials include a run-in period [28-30], typically for a duration of 1-4
289 weeks, where participants self-monitor their binge episode frequencies or are administered
290 placebo in a single-blind fashion. If participants' binge episodes persist over the course of this
291 run-in period, they have demonstrated stability of symptoms and are typically less responsive to
292 placebo [27]. We plan to use a 2-week run-in period consisting of daily monitoring of binge
293 episodes in the proposed study to ensure the stability of BED in our participants. Participants will
294 not be using a placebo during this run-in. After this run-in period, we will use a 17-week double-
295 blind placebo-controlled trial to test the efficacy of liraglutide compared to placebo in reducing
296 binge eating episodes, along with our secondary outcomes. The 17-week duration will allow for
297 titration to the 3.0 mg dose over 5 weeks, followed by a 12 week trial at the full dose, which
298 would allow for adequate time to test for efficacy of the medication on reduction in BED

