477 symptoms, as measured by the Eating Disorder Examination (interview version, 16th edition)
478 [33], their mood (using a cut score of 15 on the PHQ-9)[31], suicidality (including history of
479 suicidal ideation and behavior), as assessed at screening by a score of 4 or 5 on the Columbia-
480 Suicide Severity Rating Scale [32]), and other general psychopathology, as measured by the
481 Mini International Neuropsychiatric Interview 7.0 (MINI) [34]. Participants will be asked to
482 complete additional questionnaires including the Eating Inventory (EI) [35], a questionnaire
483 assessing demographic characteristics, Loss of Control Eating Scale (LOCES) [36] to measure
484 frequency of specific eating behaviors related to loss of control, Yale Food Addiction Scale [37]
485 to identify those most likely to be at risk for substance dependence with the consumption of high

486 fat/sugar foods, Toronto Alexithymia Scale (TAS-20) [38] as a self-report measure of features
487 associated with Alexithymia, Night Eating Questionnaire (NEQ) [39] to assess the behavioural
488 and psychological symptoms of night eating syndrome, Pittsburgh Sleep Quality Index (PSQI)
489 [40] to measure sleep patterns and sleep quality, the Food Craving Questionnaire – State (FCQ-
490 S) [41] and the Food Craving Questionnaire – Trait (FCQ-T) [41] to assess state and trait
491 attitudes towards food cravings.

492
493 The Eating Disorders Examination (EDE, 16th edition) [33] is a standardized interview devised
494 for the assessment of the psychopathology specific to eating disorders. It is considered the gold
495 standard for assessment of BED. Specifically, the EDE assesses the frequency of different forms
496 of overeating during the previous 28 days, including objective binge episodes (i.e., consuming
497 unusually large quantities of food with a subjective loss of control), subjective binge episodes
498 (i.e., subjective loss of control while eating a quantity of food not judged to be large given the
499 context) and objective overeating episodes (overeating without a loss of control). It also assesses
500 inappropriate compensatory behaviors that have occurred in the previous 28 days associated with
501 eating disorder psychopathology. The EDE yields four subscales rated on 7-point scales (0-6)
502 with higher scores indicating greater pathology: Dietary Restraint, Eating Concern, Shape
503 Concern, and Weight Concern. A Global EDE score is averaged across these four subscales.

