535 contraindications to the use of liraglutide, as detailed in the inclusion/exclusion criteria.
536

537 **Run-In Period**

538 Upon successful completion of the screening visit, subjects will be asked to not change anything
539 and eat as they normally would for 2 weeks. Once per week over these two weeks they will
540 receive a brief survey through REDcap to assess their binge eating episodes. For those without
541 internet access, study staff will call the participant to ask this information over the phone. If
542 participants report having at least one binge episode per week (a total of two or more during the
543 two weeks), they will be included in the trial. Subjects will be trained at the screening visit on
544 general guidelines for the definition of a binge episode.

545
546

Table 1. Timeline and Procedures

	Screening		RCT									
	Weeks											
	Screen	2-week run-in	Randomization/ Week 0	1	3	5	7	9	11	13	15	17
Procedures												
Informed consent	x											
Adverse events actively collected	x	x	x	x	x	x	x	x	x	x	x	x
Behavioral evaluation	x											
History and physical	x											
EKG	x											
Blood draw	x											x
Labs	x											x
Log of BED behaviors		x										
Self-reported outcomes			x	x	x	x	x	x	x	x	x	x
Medical visit			x	x	x	x	x	x	x	x	x	x
Psychological assessment of BED symptoms	x		x	x	x	x	x	x	x	x	x	x
Vital signs	x	x	x	x	x	x	x	x	x	x	x	x

547
548
549
550

Note: Shaded weeks are formal assessment weeks. Data regarding binge episodes, weight, vital signs, mood and suicide risk, and other self-reported outcomes will be collected at each medication visit, as well.

551 **Randomization Visit**

552

553 Subjects who continue to meet eligibility criteria assessed at the screening visit and during the
554 run-in period will be scheduled for a randomization visit at the Center within 3 weeks of their
555 screening.

556

557 Subjects will be randomly assigned to the two interventions in equal numbers (i.e., 1:1 ratio).
558 This will be accomplished using a computer-generated algorithm operated by the Investigational
559 Drug Service of the University of Pennsylvania. Assignment will be made from randomly varied
560 block sizes (2, 4, or 6), realizing that this method may require slightly more than 152 participants
561 to be randomized in order to achieve perfect balance between the two groups.

562

563 The subject's weight, blood pressure, and pulse will then be measured, following the methods

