660 Diagnostics.) Each blood draw will require approximately 1 tablespoon (i.e., 15 mls) of blood.
661 Blood pressure and pulse will be measured on each occasion using an automated monitor
662 (Dinamap, model 9300). Two readings will be taken on each occasion (at 1-minute intervals),
663 after participants have been seated for at least 5 minutes.

664

665 At baseline screening, participants will complete a history and physical examination and have an
666 EKG. Interpretation of results will use the categories "normal", "abnormal", not clinically
667 significant" or "abnormal, clinically significant". Subjects will be screened extensively (by a
668 physician or nurse practitioner) to determine that they have no contraindications to the use of
669 liraglutide or to possible weight loss.

670

671 **Other Assessments**

672 n/a

673

674 **Subject Compliance**

675 Subjects will be instructed to keep a medication diary to be reviewed at each visit, and they will
676 be asked if they have missed any doses since their last visit. We will also measure subjects'
677 medication adherence using injection counts from visual inspection of the dose counter taken
678 from subjects' injection pens. Subjects will be instructed to bring the pen to each session, and we
679 will record missed doses and problem solve with subjects if they are missing doses.

680

681

682 **Assessing Adverse Events**
683 All information regarding adverse events will be actively collected from the point of the first
684 study-related activity (i.e., completion of the informed consent procedure), through to each
685 participant's study endpoint. This includes adverse events that may be related to any study
686 procedure (i.e., laboratory tests or ECGs) that may not have been performed during normal
687 management of the participant, in addition to his/her use of liraglutide.
688

689 **STATISTICAL CONSIDERATIONS:**

690 **Sample Size Calculation**

691 A power analysis was conducted for the primary outcome, reduction in binge episodes per week
692 (i.e., last 7 days). Estimated variances and clinically relevant treatment differences were derived
693 from the literature using previous randomized controlled trials for BED [14, 45]. The common
694 standard deviation used was 4.1 [45], and the clinically relevant change in binge episode used
695 was 1.6 binge episodes per week [45]. Furthermore, a mixed effects model design assuming a

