696 compound symmetry covariance structure (congruent with the primary analytic plan) with a total
697 of 10 assessment points and an ICC parameter equal to 0.59 (this is the value that was used as the
698 auto correlation rho in PASS), estimated based on data collected from similar populations within
699 our Center for Weight and Eating Disorders [46], i.e., reduction in nocturnal ingestions per week
700 among patients with night eating syndrome with an SSRI. There is often overlap between
701 persons with night eating syndrome and BED and we believe that the variance in improvements
702 from week to week in core symptoms of these disorders would be similar. Based on these
703 estimates, a baseline sample size of 152 participants (76 per group) with a 15% attrition rate
704 (actual total n=132) will give 80% power to detect a clinically relevant mean difference in degree
705 of reduction in binge episodes of 1.6 per week (effect size: 0.39) to be significant at alpha = 0.05,
706 based on a two-sided test. All secondary outcomes will be considered exploratory and evaluated
707 at the alpha=0.05 level. However, those exploratory analyses will provide valuable findings on
708 changes in weight and other clinically meaningful changes in eating disordered attitudes and
709 behaviors that have not been examined previously in relation to the use of liraglutide. The power
710 analysis was conducted using the PASS software, Version 11 NCSS LLC, Kaysville, UT [47].
711

712 **Statistical Methods**

713 Preliminary and descriptive analyses. All data will first be assessed for missing and out-of-range
714 values with basic statistical procedures such as univariate statistics (means, confidence intervals,
715 standard deviations, ranges, frequencies, proportions, percentiles) and graphs such as histograms,
716 box and whisker plots, scatter plots and Q-Q plots. All questions of data quality will be
717 investigated and resolved before any statistical modelling, as complete and accurate data are
718 essential for unbiased estimates and confidence intervals.
719

720 Baseline and demographic characteristics will be summarized overall for all subjects and by
721 treatment group. Means and confidence intervals will be provided for continuous variables and
722 frequencies and percentages for categorical variables. Graphical methods mentioned above will
723 be used to examine distributions and identify potential influential points. The balance of baseline

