724 measures across the two treatment groups will be compared using appropriate 2-sample tests,
725 including Wilcoxon rank-sum and t-tests for continuous variables, and Fisher's exact and Pearson
726 Chi-square tests for categorical variables. Any baseline variables found to be associated with
727 treatment condition will be added to the outcome analysis as a covariate.

728
729 **Primary analysis.** The primary outcome is the degree of reduction in binge episodes per week.
730 It is count data that is likely to be skewed, so a shifted log transformation will be considered to
731 stabilize the distribution to better meet the normality assumptions. To address the primary aim 1,
732 a mixed effects model will be fit with Treatment Group (liraglutide 3.0 mg/d and placebo) as a
733 between subjects factor and Time (Weeks 1 through 17) as a categorical within-subjects factor.
734 Time is treated as a categorical factor so that we can use the group-time interactions with the
735 time main effect to estimate and test intention-to-treat (ITT) treatment group differences at each
736 time point, with the 17-week time point as our primary ITT test. In fitting a mixed effects model
737 with maximum likelihood, a variance-covariance structure must be selected. We will begin by
738 assuming a compound symmetry structure, but also consider criteria such as the Akaike's
739 Information Criterion (AIC) for selecting the best form of the variance-covariance structure
740 using Residual Maximum Likelihood (REML) (e.g., Compound Symmetry, Toeplitz, first-order
741 autoregressive, and unstructured). Furthermore, we will include as baseline covariates those
742 variables that have been established to be associated with the outcome based on prior literature,
743 including sex and age. The results from the mixed model will be summarized by mean (SE)
744 change from baseline for each treatment group at each time point.
745

746 Given the above definition of the ITT tests under the mixed effects model, the main interest in
747 this study is the to the test of the primary hypotheses that participants randomized to liraglutide
748 3.0 mg/d (N=76) will show superior improvements from baseline to treatment end (week 17) in
749 the number of binge episodes per week as compared to those on placebo (N=76). The primary
750 hypothesis will be evaluated at the alpha = 0.05 level and all other contrasts and

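### The primary model does not name baseline binge frequency as a covariate, and the screening and run-in counts serve eligibility only; adjusting for both would sharpen the week-17 comparison

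*Combined protocol and SAP*

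**What the plan says.** All references are to the combined protocol and SAP.

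- **Endpoints, Primary:** "The primary endpoint is change in binge episodes per week from randomization (week 0) to" study end at week 17.
- **Statistical Methods, Primary analysis:** "The primary outcome is the degree of reduction in binge episodes per week". The model has treatment group, time as a categorical factor over weeks 1 to 17, and their interaction, with week 17 as the primary test. Prognostic covariates are those known from the literature, with sex and age given as the examples. Any baseline variable found to differ between arms is also added. Baseline binge frequency is not named.
- **Screening Procedures:** the EDE interview records the frequency "of overeating during the previous 28 days, including objective binge episodes".
- **Run-In Period:** "Once per week over these two weeks they will" be surveyed on their binge episodes. Two or more episodes over the fortnight admit the participant. Rationale for Study Design describes the same run-in as daily monitoring.
- **Recall window:** Assessments for Efficacy has the interviewer ask about the period since the previous visit. Sample Size Calculation defines the outcome on the past seven days. Randomization Visit allows up to three weeks between screening and week 0.

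No section brings the screening or run-in counts into the primary analysis.

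**The concern.** A weekly binge count varies a good deal within a person. At the plan's ICC of 0.59, 41% of the variance of one weekly count is not stable between people. If the response is reduction from a short week-0 count and nothing adjusts for that count, its noise passes into the comparison at every later visit. The trial already holds further pre-randomisation counts of the same behaviour that would help predict the week-17 value.

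All these values precede allocation, so adjusting for them does not bias the comparison of arms. What is at stake is precision. The sample fell from a planned 152 to 36 and recruitment has stopped, so better use of existing data is one of the few ways left to narrow the interval.

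**Working it through.** **Inputs.** From Sample Size Calculation: ICC 0.59, compound symmetry, 10 assessments, and "standard deviation used was 4.1 [45], and the clinically relevant change in binge episode used" was 1.6 per week. From the notes on the final sample: 36 participants. Assumptions: 18 per arm, and 4.1 is the SD of a weekly count. The plan does not say whether 4.1 is the SD of a count or of a change.

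**The plan's own figure.** The stated target is "actual total n=132) will give 80% power to detect a clinically relevant mean difference in degree" of reduction of 1.6, "based on a two-sided test" at 0.05.

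- Variance factor for a mean over 10 assessments: (1 + 9 × 0.59)/10 = 0.631.
- Per arm: 2 × (1.96 + 0.842)² × 4.1² × 0.631 / 1.6² = 65.04, so 66 per arm and 132 in total.

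The 132 reproduces, but as a time-averaged contrast with no baseline adjustment. The week-17 contrast has to be worked separately.

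**Week-17 variance factors**, in units of SD², where k is the number of weekly baseline counts averaged and ρ the ICC:

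- Change from the baseline value (k = 1): 2(1 − ρ)
- Adjusted for the baseline mean: 1 − kρ² / (1 + (k − 1)ρ)

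| Analysis, ρ = 0.59 | Factor | SE at 18 per arm | Power for 1.6 |
|---|---|---|---|
| Change from a one-week week-0 count | 0.820 | 1.24 | 25% |
| Adjusted for a one-week week-0 count | 0.652 | 1.10 | 31% |
| Adjusted for three weeks (week 0 spans the run-in) | 0.521 | 0.99 | 37% |
| Adjusted for seven weeks (EDE as four, run-in two, week 0 one) | 0.463 | 0.93 | 41% |

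SE = 4.1 × √(factor × 2/18). Power is the normal probability below 1.6/SE − 1.96.

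**Reductions in variance.**

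- Week-0 adjustment against the change score: 1 − 0.652/0.820 = 20%.
- Earlier counts, if week 0 covers seven days: 1 − 0.463/0.652 = 29%.
- Earlier counts, if week 0 already spans a three-week run-in, so that only the EDE is new: 1 − 0.463/0.521 = 11%.
- For ρ from 0.3 to 0.8, the 29% becomes 15% to 37%, and the 11% becomes 7% to 13%.

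**How the covariates enter.** Under compound symmetry:

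- Response is change from week 0, and the seven-week mean is the only baseline term: 0.815, almost no gain on 0.820, because the week-0 noise stays in the response.
- Week 0 is in the model and the mean of the six earlier weeks is a second term: 0.463, whether the response is the count or the change.

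**If correlation decays.** Take AR(1) with weekly correlation 0.97, which gives 0.97¹⁷ = 0.60 between week 0 and week 17.

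- Week 0 alone: 0.645.
- Seven-week mean in place of week 0: 0.682, which is worse.
- Week 0 plus the earlier mean: 0.645, no gain and no loss apart from the degree of freedom.

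**How many week-17 values.** The dated note at the end of Statistical Methods lists one unaffected first-year completer, four later completers and ten still active, so at most 15 week-17 outcomes unaffected by the medication mis-allocation. With 7.5 per arm, the smallest SE becomes 4.1 × √(0.463 × 2/7.5) = 1.44. The mixed model also draws on earlier visits, so this is a rough guide.

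**The case against.** Measuring change from randomisation is conventional, and leaving out a precision covariate is a lost opportunity rather than an error. That is fair, and several stronger readings a reader might infer do not stand.

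- **That the earlier counts are never used.** Both serve eligibility, and the open-ended covariate rule could admit baseline frequency. They have no stated role in the primary analysis, and that is all the documents show.
- **That baseline is a single short count.** If the interviewer asks about the time since the previous visit, week 0 already reaches back over the run-in and the further gain falls to 11%. The seven-day definition in the power section points the other way, and the documents do not settle it.
- **That a pooled mean should replace the week-0 value.** The decaying-correlation case shows this can lose precision, and with a change-score response it gains almost nothing.
- **That the improvement is free.** No new data are needed, but covariates use degrees of freedom in a sample of 36. The run-in counts are also self-reported and were used for selection, which can weaken their correlation with the outcome without biasing the comparison.

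Two further doubts remain. The ICC comes from night-eating data, and the plan treats compound symmetry only as a starting structure. Also, the ten assessments in the power section match visits at weeks 0, 1, 3 and so on to 17, so week 0 may have been meant as a response, although the primary analysis says weeks 1 to 17. The 0.820 therefore rests on the change-score reading.

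**Conclusion.** The point holds as one of efficiency. The primary model works on reduction from week 0, does not name baseline binge frequency as a covariate, and leaves out counts already collected before allocation.

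Under compound symmetry with ρ = 0.59, naming week 0 is worth about 20% of the week-17 variance against a one-week change score. The earlier counts are worth a further 29% or about 11%, depending on the week-0 window, and little or nothing if correlation decays with time. These percentages do not depend on the SD; the absolute SEs do. They take 4.1 as the SD of a weekly count, and they are optimistic because fewer than 36 participants will have usable week-17 data.

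A reader might infer that better baseline use restores the trial's power. It does not: even with 18 complete participants per arm, power for 1.6 episodes rises only from about 25% to 41%. The gain is a narrower interval.

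**What to change.** Before the codes are opened, add to the primary analysis section:

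1. Week 17 stays the primary time point. The mixed model adjusts for the week-0 weekly binge rate.
2. A second covariate is the mean weekly rate from the earlier pre-randomisation counts (screening EDE and run-in reports), each divided by the weeks it covers. Week 0 stays in the model and is not replaced by a pooled mean.
3. Covariates are on the same scale as the outcome, so on the log scale if the outcome is log-transformed.
4. The recall window at week 0 and later visits is stated, reconciling the seven-day and since-previous-visit descriptions. If the week-0 interview already covers the run-in, those weeks are left out of the second covariate so that they are not counted twice.

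The cost is a few sentences, one derived variable from data in hand, and one or two degrees of freedom in a sample of 36. Apart from the extra degree of freedom, keeping week 0 and adding the earlier mean should do no worse than adjusting for week 0 alone.
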